#### 6.2 Per protocol Population

In SET centres the per-protocol population includes all randomized patients who participated in some or all the centre prescribed SET classes as defined in the protocol.

Participants who in SET centres did not attend any centre specific SET class are excluded.

For all centres (offering SET or not), participants who withdraw from the study before the primary outcome measurement at 3 months is carried out or withdraw from the study and explicitly decide to not allow use of the primary outcome data already collected will be excluded from this analysis set.

The per-protocol analyses will be carried out for the primary and secondary endpoints.

Imperial Clinical Trials Unit	STATISTICAL ANALYSIS PLAN	NESIC
-------------------------------	---------------------------	-------

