## 4. PARTICIPANT ENTRY

### 4.1 Study setting and population

This study is open to all patients at the participating NHS sites with a diagnosis of IC meeting specific inclusion and exclusion criteria.

The sites have been selected with their respect to their ability or not to provide SET.

The following six able to provide a SET programme^:

1. Imperial College Healthcare NHS Trust
2. North Bristol NHS Trust
3. Hull and East Yorkshire Hospitals NHS Foundation Trust
4. University Hospital Southampton NHS Foundation Trust
5. Dorset County Hospital NHS Foundation Trust
6. St George's University Hospitals NHS Foundation Trust\*

^Authorised SET centres will be permitted to recruit patients who do not wish to attend SET classes using a randomisation list that will allocate participants to Exercise Advice + NMES or Exercise Advice alone.

The following six are not able to provide a SET programme:

7. Cambridge University Hospitals NHS Foundation Trust
8. The Newcastle Upon Tyne Hospitals NHS Foundation Trust
9. Taunton and Somerset NHS Foundation Trust
10. Nottingham University Hospitals NHS Trust
11. The Royal Bournemouth & Christchurch Hospitals NHS Foundation Trust

\*a dual centre; a SET programme is only recommended in patients residing in the Wandsworth catchment area

Imperial Clinical Trials Unit	NESIC Clinical Study Protocol V6.0 24/03/2020	Form Number CR001A-T
-------------------------------	---	-------------------------

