**SET Centre randomisation:**

- Best medical therapy including exercise advice and supervised exercise (control 1)  
OR
- Best medical therapy including exercise advice, supervised exercise and neuromuscular electrical stimulation (treatment 1)

Authorised SET centres will be permitted to randomise patients who do not wish to attend [SET classes](#) (i.e. nonSET patients). Therefore, the authorised SET sites will act, for the purposes of these participants, as nonSET sites. In doing so they are still following the basic protocol instructions in that they are providing best medical therapy, as agreed between patient and clinicians, which in this case is not to participate in the SET classes.

At these centres, the InForm database will be linked to a SET and nonSET randomisation list. The appropriate randomisation list will be used by sites dependent on whether the patient is attending / not to attending the SET programme.

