#### **6.4.2. Withdrawal from Study**

Withdrawal from the study refers to discontinuation of study treatment and study procedures and can occur for the following reasons:

- Subject decision
- Loss to follow-up
- Subject loss of capacity

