## **5. General Considerations**

### **5.1 Study Design**

The NESIC trial is a pragmatic, multicentre two-arm randomised controlled study stratified by centre. There are 11 participating centres in England, distributed according to local therapy provision between SET and exercise advice only. Initially 5 SET centres and 6 exercise only centres recruited to the trial until all the SET sample of patients was recruited, subsequently 3 SET centres (Imperial, Bristol and Hull) also recruited patients for the exercise only group. Subject to any patient specific restrictions, all participants will receive the best medical therapy (BMT), which include exercise advice, and if the patient has cardiovascular risk factors, then they will aim to control this, e.g. smoking cessation, hypertensive medication and controlling diet.

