## 5.4 Study Population

This study is open to all patients at the participating NHS sites with a diagnosis of IC and who meet all inclusion and exclusion criteria. The 11 sites have been selected with respect to their ability to provide SET. The protocol includes a list of the recruiting centres and specifies whether the centre provides SET, or only provides exercise advice (EA).

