**Table 6 Summary of Protocol Deviation of randomised patients (ITT) by treatment**

Variables	Treatment  : NMES + EA and NMES+EA+SET N=(XX)	Control  : EA and EA+SET N=(XX)	Total N=(XX)
Protocol Deviation or Violation			
Protocol Deviation	XX (XX.X%)	XX (XX.X%)	XX (XX.X%)
Protocol Violation	XX (XX.X%)	XX (XX.X%)	XX (XX.X%)
Type of Protocol Deviation			
Device administration	XX (XX.X%)	XX (XX.X%)	XX (XX.X%)
Sampling	XX (XX.X%)	XX (XX.X%)	XX (XX.X%)
Visit outside window	XX (XX.X%)	XX (XX.X%)	XX (XX.X%)
Other, please give details	XX (XX.X%)	XX (XX.X%)	XX (XX.X%)
Other			
Break in SET classes	XX (XX.X%)	XX (XX.X%)	XX (XX.X%)
Classes did not commence within 2 weeks of randomisation	XX (XX.X%)	XX (XX.X%)	XX (XX.X%)
Device not in use	XX (XX.X%)	XX (XX.X%)	XX (XX.X%)
Height and Weight not recorded	XX (XX.X%)	XX (XX.X%)	XX (XX.X%)
Non-SET class patient (we are a SET centre)	XX (XX.X%)	XX (XX.X%)	XX (XX.X%)
Peripheral pulses not assessed	XX (XX.X%)	XX (XX.X%)	XX (XX.X%)
Received wrong treatment - patient bought own device	XX (XX.X%)	XX (XX.X%)	XX (XX.X%)
Problems with attendance to SEP class	XX (XX.X%)	XX (XX.X%)	XX (XX.X%)
Treadmill not increased as per protocol could only increase to a maximum of 7.5% and not 8%	XX (XX.X%)	XX (XX.X%)	XX (XX.X%)
Incomplete data measurement at baseline	XX (XX.X%)	XX (XX.X%)	XX (XX.X%)
Any Protocol Deviation or Violation by site			
Cambridge University Hospital	XX (XX.X%)	XX (XX.X%)	XX (XX.X%)
Dorset County Hospital	XX (XX.X%)	XX (XX.X%)	XX (XX.X%)
Hull and East Yorkshire Hospitals	XX (XX.X%)	XX (XX.X%)	XX (XX.X%)
Imperial College Healthcare	XX (XX.X%)	XX (XX.X%)	XX (XX.X%)
Newcastle Upon Tyne Hospitals	XX (XX.X%)	XX (XX.X%)	XX (XX.X%)
North Bristol	XX (XX.X%)	XX (XX.X%)	XX (XX.X%)
Nottingham University Hospitals	XX (XX.X%)	XX (XX.X%)	XX (XX.X%)
Royal Bournemouth & Christchurch Hospital	XX (XX.X%)	XX (XX.X%)	XX (XX.X%)
St George's University Hospitals	XX (XX.X%)	XX (XX.X%)	XX (XX.X%)
Taunton & Somerset	XX (XX.X%)	XX (XX.X%)	XX (XX.X%)
University Hospital Southampton	XX (XX.X%)	XX (XX.X%)	XX (XX.X%)

 Treatment: NMES + Local Available Exercise Therapy (NMES+EA and NMES+EA+SET) Control: Local Available Exercise Therapy (EA and EA+SET)

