**Table A1. Overview of the Program Information by Centre (target SET per centre)**

SET Centre	Number of sessions per week (target)	Program duration by months	Total number of sessions
*Imperial College Healthcare	1	6	24
North Bristol	2	3	24
Hull and East Yorkshire Hospitals	3	3	36
University Hospital Southampton	1	2	8
Dorset County Hospital	1	2	8
Royal Bournemouth & Christchurch Hospital	1	3	12

\*Imperial SET classes typically last 6 months so extra classes beyond 3 months will be entered under unscheduled visit

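### The protocol's untriggered causal analyses of compliance are not carried into the SAP, and neither the per-protocol set nor the complier comparison estimates the effect of using the device

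*SAP*

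**What the plan says.** SAP 6 names two populations of interest, ITT and per-protocol (PP). SAP 6.2 builds PP from two conditions and runs it for primary and secondary endpoints. In SET centres a patient must have attended at least one class: "Participants who in SET centres did not attend any centre specific SET class are excluded". In all centres, patients who withdraw before the 3-month measurement, or who refuse use of their data, are left out. Device use is not mentioned.

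Protocol 6.4.2 bears on the second condition: "Withdrawal from the study refers to discontinuation of study treatment and study procedures". A device-arm patient who stops using the device but still comes for the treadmill test has therefore not withdrawn. SAP Table 6 has a deviation row, "Received wrong treatment - patient bought own device", with no consequence for PP.

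On centre type, SAP 5.1 states that "subsequently 3 SET centres (Imperial, Bristol and Hull) also recruited patients for the exercise only group". Protocol 5.3 says of patients randomised from the non-SET list at such sites: "Therefore, the authorised SET sites will act, for the purposes of these participants, as nonSET sites".

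On compliance, Protocol 8.3 commits to causal methods covering NMES, SET and EA. Protocol 8.3.1 repeats this for NMES+EA against SET, and 8.3.2 adds a complier average causal effect (CACE) in the mechanistic evaluation. SAP 6.1 holds the SAP's only CACE, to be run if attended SET classes relative to the centre target differ between arms. SAP 8.8.1 restricts the primary and secondary endpoints to compliers. SAP 7.2 defines these as patients meeting the threshold for every assigned treatment.

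**The concern.** NMES is the only randomised component, and the protocol said that effects accounting for compliance would be estimated. A reader of the results would turn to PP and SAP 8.8.1 for that answer. PP keeps device-arm non-users who stay in follow-up, and controls who bought a device, so it dilutes the effect of use. SAP 8.8.1 compares groups selected after randomisation by different rules in the two arms, so it can show a difference when the device does nothing. The CACE, which would respect randomisation, may never run.

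The SET rule adds a practical problem. Read literally, it drops exercise-only patients at Imperial, Bristol and Hull for missing classes they were never allocated.

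**Working it through.** **Planned against carried over**

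| Protocol | SAP |
|---|---|
| 8.3: causal methods for NMES, SET and EA, no trigger | 6.1: CACE only if SET uptake differs; no cut-off, exposure, instrument or estimator |
| 8.3.1: causal comparison of NMES+EA with SET | 6.3, comparison 4: ITT Tobit regression and chi-square tests only |
| 8.3.2: CACE for mechanistic outcomes | 8.3.1: regression or ANCOVA only |

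The 6.1 trigger concerns SET patients only, half the planned sample (96 of 192). No pattern of device use can activate it.

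**Inputs.** From the plan: effect 60 m, SD 120 m, 86 per group. These reproduce: a two-sample t-test at 90% power gives 85.03, hence 86 per group, and 172/0.9 = 191.1, hence 192. The only adherence figure is the pilot's 98.5% diary use over 6 weeks in 20 patients (Protocol 1.5). It does not give the share of users or threshold-passers over 12 weeks, so I show 50 to 98.5%. All other adherence and prognosis inputs are assumptions.

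**PP dilution**, if users gain 60 m and non-users nothing, with user share p:
- no non-user withdraws: 60p = 30, 42, 57 and 59.1 m at p = 0.50, 0.70, 0.95 and 0.985;
- half of non-users withdraw before 3 months: 60p/(p + (1 − p)/2) = 40.0, 49.4, 58.5 and 59.5 m.

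**Complier comparison under zero device effect.** Simulation with an adherence factor; 60% meet EA and 60% meet SET; loading 0.5 to 0.7; correlation of the factor with AWD 0.2 to 0.5; baseline to 3-month correlation 0.7. Adjusted for baseline AWD and averaged over SET and non-SET strata, the bias is about 2 to 5 m if 50% meet the NMES threshold, 1 to 3 m at 70%, at most 0.6 m at 95%, and about 0.1 m at 98.5%. It is zero if adherence is not prognostic. Without baseline adjustment and with somewhat different assumptions (60 to 80% meeting NMES), the range is 0 to 14.4 m.

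At 50 to 70%, compliers number 25 to 37 in the device arm and 43 to 45 in control. The half-width is 1.96 × 120 × √0.51 × √(1/n₁ + 1/n₀): 42 m for 25 and 43, and 37 m for 37 and 45. The factor √0.51 is √(1 − 0.7²).

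**CACE precision.** The ITT half-width is 1.96 × 120 × √0.51 × √(2/86) = 25.6 m. Divided by user share: 26.0 m (98.5%), 27.0 m (95%), 36.6 m (70%), 51.2 m (50%).

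**A device threshold in PP, for comparison.** In the same simulation, requiring the device arm alone to pass a threshold gives an adjusted bias of 2.9 to 10.4 m if 50% pass and 1.6 to 6.7 m if 70% pass. At 50% that is roughly double the complier comparison.

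**Places that must agree before any of this can be programmed**
- Bournemouth is in the Protocol 4.1 list headed "The following six are not able to provide a SET programme", to which SAP 5.4 defers, and SAP 5.1 counts five SET centres. SAP Tables A1 and A6 list six, with a SET target for Bournemouth.
- St George's, a dual site, has no row in Tables A1, A5 or A6.
- Table A5 gives no EA threshold for Hull, so complier status is undefined there.
- SAP 8.8.1 cites 8.9.6.4 for the definition of compliance; that section holds table shells, and the definitions are in 7.2 and Appendix 3.
- For patients with diabetes, Protocol 5.5.4 gives a minimum of two 30-minute sessions a day: 60 × 84 = 5040 minutes. SAP 5.2.2 and 13.3.3 use 2520 for everyone. The 1890-minute threshold is 75% of one and 37.5% of the other.

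**The case against.** The strongest reply is that little turns on this. The primary analysis is ITT, and no success rule uses PP or SAP 8.8.1. Protocol 8.3.1 says only that PP analyses will be done, so SAP 6.2 contradicts nothing there. The SAP does not ignore device use either: 8.8.1 applies a 75% NMES threshold. The one adherence figure available is high, and near it both the dilution and the bias are negligible. All of this stands, and it limits the severity.

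Four stronger readings are tempting and are not supported.

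- *Exercise-only patients at three centres are wrongly excluded from PP.* SAP 6.2 refers to SET classes as the protocol defines them, and Protocol 5.3 treats those sites as non-SET for these patients. Under that reading nobody is wrongly excluded, and the SAP gives no count. SAP Table 6 lists a non-SET-class patient at a SET centre as a deviation, so the wording still needs repair.
- *SAP 8.8.1 was meant to replace the CACE.* It is labelled a sensitivity analysis and says no such thing. It is merely one of the two compliance analyses that run unconditionally.
- *The SAP has dropped CACE altogether, or barred it for NMES.* A conditional version remains in 6.1 with its exposure unspecified. The fault is the trigger and the missing specification.
- *PP should gain a device-use threshold.* That is the same post-randomisation selection, with larger bias in the figures above.

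A further fair point is that a CACE is not free of choices. If exposure is any home use and nearly everyone uses the device a little, it comes close to ITT. If exposure is the 75% threshold and those below it still get 40% of the benefit, a 60 m effect is overstated: at 50% passing, 60 × (0.5 + 0.5 × 0.4)/0.5 = 84 m. The exposure has to be fixed and its limits stated.

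**Conclusion.** The concern holds as a gap between protocol and SAP in the supportive analyses. The protocol's untriggered causal analyses are not carried over, and the analyses that run unconditionally do not validly estimate the effect of device use. That conclusion rests on the text alone.

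The size is uncertain. It ranges from negligible near 98.5% use to a halved effect in PP if half the device arm never uses the device, which is a stress case. The complier-comparison bias is small beside its own interval throughout the range shown. A reader should not infer that the trial's main result or sample size is in doubt; both are unaffected. Severity: minor to should-fix.

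**What to change.** 1. **Make the CACE unconditional, on the ITT set.** Use randomised arm as instrument and recorded NMES home use as exposure, defined in advance (any recorded use avoids the threshold problem above). Adjust for baseline AWD (for other outcomes, their own baseline value), centre and group. Apply it to 3-month AWD, to the mechanistic outcomes and to the secondary endpoints that SAP 8.8.1 now covers. For the mechanistic outcomes use resting readings only: both arms have them, whereas the device-arm mean in SAP Table 39 averages five readings, some taken during use. Name the estimator, state how it handles the 790 m cap, and give the missing-diary rule. State the exclusion restriction, which matters in an unblinded trial, and keep SET uptake as a check on it instead of as the trigger. Either carry over the Protocol 8.3.1 causal comparison of NMES+EA with SET or record that it is dropped.
2. **Keep complier results as description only**, and correct the SAP 8.8.1 cross-reference to 7.2 and Appendix 3.
3. **In SAP 6.2, apply the SET-attendance condition only to patients randomised from the SET list.** Label PP supportive and say that it does not estimate the effect of device use. Do not add a device-arm-only threshold.
4. **Reconcile** Bournemouth and St George's between Protocol 4.1 and SAP Tables A1, A5 and A6; the missing EA threshold for Hull; and the minimum device use in patients with diabetes between Protocol 5.5.4 and SAP 5.2.2 and 13.3.3.

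The cost is SAP wording, some programming and less precision: a CACE half-width of about 26 m at 98.5% users, rising to 51 m at 50%, against about 26 m for ITT, under the assumed baseline correlation of 0.7.

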### 6.3 Subgroup Analysis

Subgroup analysis will investigate the effect of the intervention among NMES+SET+EA, NMES+EA, SET+EA, EA. We will estimate the treatment effect in the following subgroups comparisons:

- Subgroup analysis 1: Treatment effect in SET sites vs non-SET sites (NMES+SET+EA & SET+EA vs NMES+EA & EA).
- Subgroup analysis 2: Treatment effect of NMES in the SET sites (NMES+SET+EA vs SET+EA)
- Subgroup analysis 3: Treatment effect of NMES in the non-SET sites (NMES+EA vs EA)
- Subgroup analysis 4: Investigate if the treatment effect of (NMES+EA) has a similar effect as (SET+EA)
- Subgroup analysis 5: Determine if (NMES+SET+EA) is more effective than (NMES+EA)

The subgroup analyses will be on an ITT basis and only for the primary outcome measure at 3 months.

## 7. Variables for Analysis

### 7.1 Baseline Demographic Variables

The patient baseline and demographic characteristic data will be collected, on all patients, once a written consent is obtained. The information collected includes:

- Age
- Gender
- Ethnicity
- Working Status
- Performance limited due to IC
- Lifestyle (Smoking and alcohol consumption).
- Medical History
- Pregnancy
- Concomitant medication
- Pulse
- Blood Pressure
- Body Mass Index (BMI)
- Treadmill test results

### 7.2 Derived Variables

The following variables will be calculated using specific formulas or by using special software (see Appendix 2 - 13.2).

- Intermittent Claudication Questionnaire (ICQ) score
- Short Form 36 (SF-36) scores. There are two possible ways to obtain these scores.

#### Section scores

- Physical function score
- Role-Physical score
- Body pain score
- General Health score
- Vitality score
- Social functioning score
- Role-Emotional score
- Mental Health score

#### Summary scores

- Physical components score (PCS)
- Mental component score (MCS)

Imperial Clinical Trials Unit	STATISTICAL ANALYSIS PLAN	NESIC
-------------------------------	---------------------------	-------

- **Compliance Classification**

We have classified a participant as “compliant” if they have done at least 75% of the recommended target minutes for Device use, at least 75% of the recommended EA minutes performing exercises and attend at least 50% of SET sessions by the end of the treatment period. Then compliance can be dichotomised, coding “Yes, complied” if the patient complied with the recommended threshold treatment and “No” if patient did not comply. This classification is obtained by combining the compliance classification of the three instruments used to collect compliance information from each intervention (Device, SET and EA). Procedures for these classifications are outlined in Appendix 3 section 13.3).

For each treatment group, a patient is considered compliant if they are compliant for all of their assigned treatments. Therefore, for each of the treatment groups compliance is defined as follows:

- EA: compliant if done 75% or more of recommended level of EA (75% of minutes performing exercises recommended by centre)
- EA + SET: compliant if done 75% or more of recommended level of EA and attended 50% or more SET sessions held by centre.
- EA + NMES: compliant if done 75% or more of recommended level of EA and done 75% or more of recommended level of NMES usage
- EA + SET + NMES: compliant if done 75% or more of recommended level of EA, attended 50% or more SET sessions held by centre and done 75% or more of recommended level of NMES usage

These variables, excluding compliance classification, will be summarized at follow up time periods by treatment group using the ITT analysis set. Compliance classification will be summarised at the end of the intervention period. Summaries of continuous variables will be presented as mean and standard deviations if normally distributed, and as mean and inter-quartile ranges for skewed data. Categorical variables will be presented as frequencies and percentages.

### **7.3 Primary Endpoint variable**

Absolute walking distances (AWD) at baseline, 3, 6 and 12 months (measured in metres).

For participants who walked more than 15 minutes on the treadmill during any follow up, their AWD will be censored at 790 metres. It was communicated directly to the sites that 790 metres will be used as a censored value.

In cases that the AWD is recorded when the patient walked more than 15 minutes during the study assessment (at baseline) the patient will be removed from the analysis.

In cases that the AWD is recorded at 3, 6 or 12 months with a value equal to or greater than 790 metres the value will then be censored at 790m.

### **7.4 Secondary Endpoint variables**

- Initial claudication distance (ICD) at baseline, 3, 6 and 12 months.
 

For participants that walked more than 15 minutes, their ICD will be censored at 15 minutes. The ICD at this point will be recoded as 790 metres (same procedure used to censor cases in AWD will be applied for the ICD)
- The proportion of patients who improved AWD at each time point by
  - 60 metres or more from baseline
  - 100 metres or more from baseline
- The proportion of who improved ICD at each time point by
  - 60 metres or more from baseline
  - 100 metres or more from baseline
- Quality of life scores measured at baseline, 3, 6 and 12 months
  - Recorded ICQ Health score (calculated using the formula in Appendix 2 - Section 13.2.1)
  - Recorded EQ-5D-5L Health state score [7]

Imperial Clinical Trials Unit	STATISTICAL ANALYSIS PLAN	NESIC
-------------------------------	---------------------------	-------

- Short Form 36 (SF-36) scores (Using Health Outcome Scoring Software 4.0 see section 13.2.2) [8]

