**5.4 Other baseline investigations**

Imperial Clinical Trials Unit	NESIC Clinical Study Protocol V6.0 24/03/2020	Form Number CR001A-T
-------------------------------	---	-------------------------

- **Demographic information & vital signs:** age, ethnicity, date of birth, lifestyle, socioeconomic status, weight, height, blood pressure, pulse
- **Treadmill:** The Gardner-Skinner graded treadmill test will be used (15). The treadmill will start at 3.2 km/h at a 0% incline. Every 2 minutes, the gradient of the treadmill will increase by 2%. Patients will indicate the start of their claudication pain, which will be recorded as the Initial Claudication Distance (ICD) and finally stop the test at the point the patient does not want to continue due to lower limb pain; this is the Absolute Walking Distance (AWD). The patient will not be given a final score to prevent bias. If patients are able to walk for longer than 15 minutes on the treadmill, they will be excluded from the trial.
- **Quality of Life questionnaires:** The validated EuroQoL (EQ-5D-5L) questionnaire and Short Form-36 (SF-36) questionnaire will be used to assess the generic QoL and will allow economic assessment based on intervention and score improvement. The validated Intermittent Claudication Questionnaire (ICQ) will be used to assess change in disease-specific QoL. These should be completed prior to informing the participant of the treatment allocation to prevent bias.
- **Haemodynamic assessment**
  - **Duplex ultrasonography:** Using the appropriate arterial ultrasound probe and pre-set volume flow algorithms on a duplex ultrasound machine, flow within the common femoral artery (CFA), preferably of the most affected limb, will be measured, approximately 5cm below the mid-inguinal point at the groin. Measures include volume flow (VF, cc/min) and time-averaged mean velocity (TAMV, cm/s).
    - **In the control group:** only resting values will be undertaken over a 3-minute period.

Imperial Clinical Trials Unit	NESIC Clinical Study Protocol V6.0 24/03/2020	Form Number CR001A-T
-------------------------------	---	-------------------------

- **The intervention group** will have these parameters measured at rest, at 15 and 30 minutes into device use and then at 1 and 5 minutes after device cessation (16).

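### SAP 7.4 triggers ICD censoring on total walking time rather than on absence of pain, so read literally it can replace an observed pain-onset distance with a censored 790 m

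*SAP*

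**What the plan says.** Protocol 5.4 takes two distances from one treadmill test. For pain onset: "Patients will indicate the start of their claudication pain, which will be recorded as the Initial Claudication Distance (ICD"). AWD is the distance at which leg pain makes the patient give up. The first is normally known before the second.

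SAP 7.4 gives the ICD rule: "For participants that walked more than 15 minutes, their ICD will be censored at 15 minutes". Such an ICD is then set to 790 m. A bracketed note refers back to the rule for walking distance: "same procedure used to censor cases in AWD will be applied for the ICD".

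That AWD procedure, in SAP 7.3, has two limbs at follow-up. One is triggered by time: "For participants who walked more than 15 minutes on the treadmill during any follow up, their AWD will be censored at 790 metres". The other is triggered by the recorded value and begins: "In cases that the AWD is recorded at 3, 6 or 12 months with a value equal to or greater than 790 metres". It resets any such reading to 790 m. Patients who walk more than 15 minutes at baseline are excluded or removed.

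Table 2 describes ICD itself as censored at 15 minutes, with 790 m as the distance at that point. Section 8.3.1 analyses the censored ICD with a multilevel Tobit model. Tables 25 and 26 describe the proportions improving in ICD by 60 m and 100 m.

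**The concern.** For AWD a time trigger is sound, because someone still walking at 15 minutes has an unobserved stopping distance. ICD is different. A patient with pain at 300 m who walks past 15 minutes has a known ICD of 300 m. The sentence in 7.4 would record 790 m, and the Tobit model would read that as a true ICD of at least 790 m, which the data contradict.

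The recode works only at follow-up, since baseline ICD is untouched. If NMES lengthens AWD and so brings more NMES patients to the cap, their ICD rises with no change in pain onset. Part of the AWD effect then appears a second time as an ICD effect. The ICD improvement proportions shift the same way: any recoded patient with a baseline ICD of 690 m or less passes both thresholds (790 − 690 = 100 m).

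**Working it through.** **1. The plan's own figure.** The only sample size stated is for AWD (SAP 5.7): difference 60 m, SD 120 m, two-sided 5%, 90% power.
- Normal approximation: n = 2 × (1.960 + 1.282)² × 120² / 60² ≈ 84.1, so 85 per arm.
- Exact two-sample t-test: power 0.8999 at 85 and 0.9032 at 86, so 86 per arm, or 172.
- With 10% dropout: 172 / 0.9 = 191.1, so 192.

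Both figures reproduce. No power is stated for ICD.

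**2. The cap.** Protocol 5.4 says "The treadmill will start at 3.2 km/h at a 0% incline", and only the gradient is said to rise. At constant speed, 15 minutes is 3,200 / 60 × 15 = 800 m, and 790 m is reached at 14.8 minutes. The time and distance triggers are therefore close but not identical.

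**3. Share at the cap under the planning assumptions.** With normal AWD, SD 120 m, the share above 790 m is about 0.00004% for a control mean of 200 m and 0.0005% for a treated mean of 260 m. On those figures the rule touches almost nobody.

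**4. Plain-mean arithmetic.** If recoded values are averaged as ordinary numbers, shift = (excess share at cap) × (790 − true ICD). For an assumed true ICD of 250 m:
- 2-point excess: 0.02 × 540 ≈ 11 m
- 5-point excess: 0.05 × 540 = 27 m
- 10-point excess: 0.10 × 540 = 54 m

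This bears on raw means. It is not the planned Tobit estimate.

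**5. Simulation of a Tobit estimate.** There was no true ICD effect. Each scenario had 1,000 trials of 86 per arm, with a single-visit Tobit at 790 m adjusted for baseline ICD. Assumptions: lognormal AWD, an additive AWD effect, ICD averaging half of untreated AWD, and correlation 0.6 with baseline. The pain-based rule censors only an ICD that itself reaches 790 m. The literal rule sets 790 m whenever AWD reaches the cap.

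| Control AWD mean/SD (m) | AWD effect (m) | At cap, control / NMES | ICD effect, pain-based rule (m) | ICD effect, literal rule (m) | False positives, pain-based / literal |
|---|---|---|---|---|---|
| 200/120 | 60 | 0.3% / 0.5% | +0.1 | +0.8 | 5.4% / 4.9% |
| 300/200 | 60 | 2.8% / 3.8% | +0.1 | +4.4 | 6.4% / 6.3% |
| 400/250 | 60 | 7.0% / 9.1% | −0.4 | +9.2 | 4.0% / 5.6% |
| 450/300 | 60 | 11.0% / 13.3% | −0.6 | +10.9 | 5.6% / 6.0% |
| 450/300 | 100 | 11.0% / 16.0% | −0.2 | +25.9 | 4.8% / 10.5% |
| 400/250 | 0 | 7.1% / 7.1% | −0.4 | −0.5 | 3.6% / 4.6% |

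The Monte Carlo standard error of a 5% rate is √(0.05 × 0.95 / 1,000) ≈ 0.7 points. The literal-rule rates at 60 m cannot be told apart from 5%, but 10.5% can.

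Under the literal rule, the between-arm difference in the proportion improving ICD by 60 m was 0.1 to 0.5 points for a 60 m AWD effect and 1.7 points for 100 m. Under the pain-based rule it was −0.3 to 0.0 points in the same scenarios. The 100 m proportion was not simulated.

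**The case against.** **The literal reading is not the only one.** Censoring a variable at a limit usually affects only values at or beyond it. The bracketed cross-reference could import the value-based limb of 7.3, which would touch only an ICD of 790 m or more, and Table 2 fits that. This stands, and it is why the point concerns wording that permits the error. It does not remove the point: the sentence in 7.4 mirrors the time-based limb, no text protects an observed ICD, and two programmers could build different ICD datasets from the same SAP.

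**Few patients may reach the cap.** That is true under the planning assumptions. Against it, SAP 5.5.2 records that walking beyond 15 minutes was made an exclusion by amendment, and 8.2 adopts Tobit specifically to deal with the cut-off. The plan evidently expects some ceiling cases.

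**Stronger inferences that the documents do not support.**
- A reader might infer that everyone walking past 15 minutes loses an observed ICD. Those with no pain by then are properly censored.
- A reader might infer that the rule manufactures an ICD benefit. That needs a true AWD effect and unequal shares at the cap.
- A reader might take 54 m as the likely size. It needs a 10-point excess with pain at 250 m, for which the documents give no basis, and it is not a Tobit estimate.
- A reader might call every recoded patient a false responder. Some will truly have improved, and the ICD proportions are descriptive, with no test planned.
- A reader might treat ICD as the leading secondary endpoint because it is listed first. The list sets no order of testing.

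**Conclusion.** The point holds as a defect of wording with a conditional consequence. SAP 7.4 keys ICD censoring to walking time. Applied literally, it discards a recorded pain-onset distance and biases the ICD comparison towards NMES whenever NMES improves AWD and more NMES patients reach the cap.

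At the trial's 60 m target effect the simulated bias is about 1 to 11 m, with no clear inflation of false positives. It becomes material (about 26 m, 10.5% false positives) only in the scenario with a 100 m AWD effect and 11% against 16% at the cap. Without an AWD effect there is no bias.

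These sizes rest on the assumed AWD and ICD distributions, and on one visit in place of the full multilevel model. The documents give neither a ceiling rate nor an ICD distribution. The primary endpoint, its model and the sample size are unaffected. It should be fixed, but it does not threaten the trial's main conclusion.

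**What to change.** Reword SAP 7.4 and the ICD row of Table 2 so that ICD is right-censored at the 15-minute/790 m limit only when no claudication pain was reported by then. Where pain onset was recorded earlier, keep the recorded ICD even if AWD is censored. State whether time or distance defines the limit, since 790 m falls slightly before 15 minutes. Drop the cross-reference to the AWD procedure, or limit it to the value-based limb.

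Before database lock, check that sites entered the actual pain-onset distance for patients who reached the cap, and not 790 m. Section 7.3 says that sites were told of the 790 m value.

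The cost is a sentence or two in the SAP, one line of derivation code and a short data query. Protocol 5.4 already requires pain onset to be recorded, so no new measurement is needed.
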